6.5.5.2 Reactions to Dosing at Home (Groups 1 and 2)

With the occurrence of symptoms of an acute reaction to study product after home-dosing, or any acute allergic reaction, subjects/parents or guardians are instructed to call the study site. The investigator must then determine whether or not the dose was tolerated ([Section 6.5.3](#)). Because of the reduced reliability inherent in the second-hand reporting of symptoms, investigators are strongly encouraged to have subjects return to the clinic to undergo dosing under direct observation whenever acute allergic symptoms associated with dosing are reported.

When symptoms of a dose-related allergic reaction are reported during the course of daily home-dosing, the investigator must assess the severity of the reaction and whether the dose associated with the reaction was tolerated. The appropriate intervention will depend on the type and severity of symptoms ([Section 6.5.5](#)).

In general, moderate or severe symptoms will be considered clinically significant, and any dose eliciting such symptoms *assessed as not tolerated*; however, mild symptoms may also be considered clinically significant (eg, if affecting multiple organ systems, increasing in intensity, occurring with increasing frequency, or affecting a larger area over time), and *assessed as not tolerated*. Whenever there is question as to the clinical significance of mild signs or symptoms, the investigator should have the subject return to the CRC for observed dosing under medical supervision.

For home-doses *assessed as not tolerated* based on acute dose-related symptoms, the same procedures described in [Section 6.5.5](#) for adjusting up-dosing should be followed.

The recurrence of mild symptoms over the course of several days of home-dosing should suggest that the dose level is not tolerated, even if each individual occurrence of symptoms could be assessed as tolerated based on the criteria listed above. In this circumstance, investigator judgment will be required to determine the best course of action with the possible actions being the following:

- Continue with daily home dosing at the current dose level.
- Continue the same daily dose for the rest of the 2-week interval, with the dose split into 2 fractional doses given 8 to 12 hours apart (the 2 fractional doses need not be equal).
- Return to the CRC for repeat dosing at the current dose level under direct observation to confirm whether or not the dose level is tolerated.
- Return to the CRC for dosing of a previously tolerated dose level, either a 1- or 2-step reduction (per investigator judgment, based on severity of reaction) and follow the procedures described in [Section 6.5.5.2](#) above.
- Institute the 4-week hiatus from dosing, with resumption of dosing at the 3 mg/d dose level, as permitted for recurrent GI symptoms occurring at or before the 20-mg dose, as described in [Section 6.5.3.2](#).
- Discontinuation of dosing.

[figure not shown]
Any subject who discontinues up-dosing due to severe or repeated allergic reactions to study product should have his/her mechanistic blood draw and CBC ([Section 6.4](#)) at, or as soon as possible to, the time of the last dose and no later than at his or her Early Discontinuation Visit.

Home dosing symptoms during nondaily EM regimens are handled separately and discussed further in [Section 6.5.7](#).

6.5.5.3 Dose Adjustment in Response to Intercurrent Adverse Events (QD Regimens only)

At the investigating physician's discretion, temporary dose reductions, ranging from a 1-step reduction (ie, to the previous dose) to approximately half of the current dose level (to the nearest feasible available whole dose), can be instituted as part of the treatment regimen for an intercurrent AE. Also, if a pattern of decreased tolerability of study product during menses is discerned, then a temporary dose reduction can be instituted during this time. A schematic showing procedures for temporary dose reductions due to intercurrent AEs is provided in [Figure 4](#); explanatory text follows the figure.

Figure 4: Schematic for Temporary Dose Reductions due to Intercurrent Adverse Events (QD Regimens Only)

CRC = clinical research unit; QD = daily.

- For dose reductions of ≤ 4 consecutive days, whether dose re-escalation is to occur at home or in the CRC is at the investigator's discretion. If the reduction in dose is maintained for ≤ 4 consecutive days, then the pre-reduction dose level may be resumed, with the biweekly escalation schedule kept unaltered.
- If a reduction in dose is maintained for 5 to 7 consecutive days, then the subject is to return to the CRC to undergo dosing under medical supervision. At the investigator's discretion, the pre-reduction dose level may be resumed or dosing may continue at the reduced dose level. The biweekly escalation should be reset so that the subject receives ≥ 2 consecutive weeks of treatment at the dose level assigned (either the reduced or the pre-reduction dose level).
- If a reduction in dose is maintained for 8 to 14 consecutive days, then the next escalation attempted must be conducted in the clinic, and it should only be to 1 dose level above the reduced dose. If the escalation is successful, the subject should continue home-dosing for a minimum of 2 weeks, with his or her biweekly escalation schedule reset as necessary.

Doses of study product may also be withheld at the investigator's discretion, in response to an intercurrent AE. Doses withheld as part of the treatment for an AE constitute a special category of missed peanut OIT doses ([Section 6.6](#)).

6.5.6 Treatment for Reactions During the Up-dosing Period: Pharmacological and Supportive Treatments

The treatment(s) for types of reactions during the Up-dosing period are summarized by severity of reaction in [Table 6](#).

Table 6: Treatment(s) for Reactions during the Up-dosing Period by Severity of Reaction

Reaction Severity ^a	Treatment(s)
Mild acute allergic reactions requiring treatment	Antihistamines
Moderate acute symptoms requiring treatment	Antihistamines and/or epinephrine, as indicated
Severe symptoms	Antihistamines and/or epinephrine, as indicated

Assessment of severity of reaction is described in [Section 6.5.1](#). Assessment of tolerability of an individual dose is described in [Section 6.5.2](#).

- Treatment of acute reactions should be with either an antihistamine and/or epinephrine, along with IV fluids, a beta-agonist (eg, albuterol, by inhaler or nebulizer), oxygen, and/or glucocorticosteroids, as indicated. Many mild acute allergic reactions can be transient and self-limiting, requiring no therapeutic intervention. Others, however, may require treatment. Generally, for mild symptoms requiring treatment, the subject should receive antihistamines.
- Acute allergic reactions manifesting with moderate symptoms will generally require therapeutic intervention, although some, even moderate, symptoms may on rare occasion be so transient as to require no specific treatment. Generally, for moderate symptoms requiring treatment, the subjects should receive antihistamines and/or epinephrine, as indicated. If there is uncertainty as to the severity of the reaction, administering epinephrine would be considered the most appropriate course of action.
- Generally, severe symptoms will require treatment with epinephrine at a minimum. If severe symptoms that qualify as stage 3 anaphylaxis (as defined in [Appendix 3](#)) occur at any time, dosing with study product will stop and the subject will be discontinued from the study as an escalation failure nonresponder.

The procedures(s) that should be implemented after treatment of a reaction experienced during the Up-dosing period are summarized in [Table 7](#). An explanation follows the table.

Table 7: Procedure(s) Following Treatment of a Reaction Experienced during the Up-dosing Period

Treatment Given for Reaction	Procedure(s) Following Treatment
Antihistamines only	
 Continue dose escalation
Epinephrine: ≥ 2 doses taken either in CRC or at home	
 Discontinue dosing Subject returns to CRC 14 days after last dose for Early Discontinuation Visit
Epinephrine: single dose given in CRC	
 Stop dosing at CRC Reduce next dose by 2 doses, both to be administered at CRC Continue bi-weekly escalation
Epinephrine required for a second consecutive time during, or after, 1 escalation attempt	
 Dose reduced by 2 dose levels. Reduced dose level continued for 6 to 8 weeks Escalation may be attempted after 6 to 8 weeks
Epinephrine required for a third consecutive time during an escalation attempt	
 Discontinue dosing Subject returns to CRC 14 days after last dose for Early Discontinuation Visit
Epinephrine: single dose at home	
 Not counted in the total count of epinephrine uses unless severe anaphylaxis has occurred Subject returns to CRC for an observed dose under medical supervision prior to resuming any dosing at home

CRC = clinical research center.

- Antihistamines
If a subject receives antihistamines only, the dose escalation can be continued. If epinephrine is administered, then a different course of action is to be taken (see below).
- Epinephrine – General Procedures
Any reaction to study product (in clinic or at home) that requires more than 2 doses of epinephrine will halt all further dosing of study product for the individual. The subject will be asked to return to the CRC 14 days following the last dose of study product to undergo an Early Discontinuation Visit ([Section 6.3.10](#)).
- Epinephrine – Single Dose Administered at Clinic
If a single administration of epinephrine is required during or after a dose-escalation in the clinic, no further dosing of study product is to occur at that visit. The next dose of study product is to be reduced by 2 dose levels and administered in the CRC, but biweekly dose escalation should continue.
If a single administration of epinephrine is required for a second consecutive time during, or after, 1 escalation attempt, the dose should be reduced by 2 dose levels, and the subject continued at that dose level for 6 to 8 weeks. After 6 to 8 weeks at the reduced dose, an escalation attempt may be tried in clinic.

If a *single administration of epinephrine is required for a third consecutive time* during an escalation attempt, no further dosing should be attempted. Dosing in these subjects will be discontinued. They will be asked to return to the CRC 14 days following their last dose of study product to undergo an Early Discontinuation Visit (Section 6.3.10).

- Epinephrine – Home

If a single administration of epinephrine is given during dosing at home, this epinephrine use is not counted as one of the uses described above, unless severe anaphylaxis is assessed to have occurred at home. Administration of epinephrine outside of the clinic should be followed immediately by the subject being taken to the nearest emergency department. The subject should return to clinic for an observed dose under medical supervision prior to resuming any dosing at home.

6.5.7 Reactions Occurring During the Maintenance and Extended Maintenance Periods (Groups 1 and 2)

Dosing guidelines following treatments given for reactions experienced by subjects in Groups 1 and 2 receiving AR101 at 300 mg QD, QOD, BIW, QW, or QOW during the Maintenance and Extended Maintenance period are summarized in [Table 8](#). A textual explanation follows the table.

Table 8: Dosing Guidelines Following Treatment for Reactions Experienced by Subjects in Groups 1 and 2 Receiving AR101 at 300 mg QD, QOD, BIW, QW, or QOW During Maintenance and Extended Maintenance

Treatment Regimen	Dosing Guidelines and Procedures
QD	Follow Up-dosing procedures.
QOD, BIW, QW, or QOW	
Withhold the scheduled dose until the AE is resolved and the dose can be safely administered.Reset the interval between doses after the subsequent dose is tolerated.
If the dose must be withheld for > 3 days past when the dose was due to be taken, the investigator must discuss the case with the Sponsor's Medical Monitor prior to administering the next dose. Dosing options are described in the text following this table.

BIW = twice weekly; QD = once daily; QOW = every other week; QW = once weekly.

- This phase consists of the subject receiving the 300-mg dose of study product either QD, QOD, BIW, QW, or QOW. For any symptoms noted during the QD Maintenance or EM period, the same study product dosing guidelines and procedures

for QD dosing will be followed as for the Up-dosing Period. However, for subjects on nondaily regimens, the following guidelines and procedures apply:

[figure not shown]
- The tolerability of doses on nondaily dosing regimens will be evaluated as in [Section 6.5.2](#), keeping in mind the individual stopping rules related to tolerability and symptom severity as outlined in [Section 7.8.2](#).
- In the event of a clinically significant intercurrent AE occurring at the time of a scheduled QOD, BIW, QW, or QOW dose, subjects should be advised to withhold the scheduled dose until the AE is resolved and the dose can be safely administered; the interval between doses should be reset once the subsequent dose is tolerated.
- *If the dose must be withheld for > 3 days past when the dose was due to be taken*, the investigator must discuss the case with the Sponsor's Medical Monitor prior to administering the next dose. Options available at that time include, but are not limited to, any of the following:
 1. Continue ARC004 and administer the next 300 mg dose under supervision at the CRC.
 - If tolerated, continue EM dosing at 300 mg on the same schedule, resetting the dosing interval;
 - If not tolerated, consider options 2 or 3 below.
 2. Continue ARC004 and administer approximately half of the 300 mg dose under supervision at the CRC. The entire 300 mg dose should be prepared with the preferred vehicle and then approximately half of the dose should be administered; *the remainder should be discarded*. If not tolerated, the subject should be discontinued from the study. If tolerated, up to 3 successive doses can be administered this way according to the subject's assigned schedule, but then 300 mg should again be attempted.
 3. Discontinue the subject from ARC004 and consider enrollment in ARC008 if the site has received approval to enroll subjects in ARC008. This should be the preferred option for any subject on a QOD, BIW, or QW dosing regimen whose interval between AR101 doses exceeds 14 days. If the subject is at a site that has not yet received approval to enroll subjects in ARC008, the subject may start AR101 daily dosing and have visits in the Repeat Up-dosing Period in ARC004 until ARC008 is available.
- For subjects having acute reactions to QOD, BIW, QW, or QOW doses, appropriate treatment and follow-up is to be administered per [Section 6.5.6](#). As mentioned in [Section 7.8.2](#), any EM subject on QOD, BIW, QW, or QOW dosing having 1 related SAE; 1 related AE graded severe; 2 related AEs occurring on separate occasions, both graded moderate; or 3 consecutive doses judged "not tolerated," will be considered as a treatment failure and discontinued from ARC004 for safety reasons. Such subjects may be eligible to enroll in ARC008 and return to a QD regimen. If a site has not yet received approval for enrollment of subjects in ARC008, the subjects may start AR101 daily dosing and have visits in ARC004 until ARC008 is available, then continue dosing in ARC008.

- Sites will ensure that all subjects have in-date epinephrine autoinjectors, appropriate anaphylaxis teaching, and access to emergency services as per local standards.

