- Temporarily withholding study product dosing – this may be instituted as treatment for an intercurrent AE or to aid the investigator in determining if a dose level is or is not tolerated, but the duration of withholding study product may not exceed 14 consecutive days, or the subject will be discontinued from the study. The manner in which dosing may resume after withholding dosing of study product depends on the duration for which dosing was withheld.
- Reducing dose by 2 dose levels and maintaining the reduced dose level for ≥ 6 weeks – continuing dosing at a reduced dose level for ≥ 6 weeks prior to attempting re-escalation is mandatory if 2 doses of epinephrine are given to treat a single AE.
- Stopping dosing and discontinuing the subject early from the study – this is an option that the subject may elect at any time and for any reason. The investigator must discontinue the subject from further dosing and continuation in the trial under circumstances that could jeopardize the health of the subject or the integrity of the trial.

[figure not shown]

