- Severe symptoms (these always indicate lack of tolerability): If *severe symptoms* occur, the action should be to treat the subject for the allergic reaction, and then, in consultation with the Medical Monitor, decide whether or not to discontinue the subject from the study. If it is determined that it is safe to allow the subject to continue in the study, the subject should return to the CRC the next day for dosing at a 2-step reduction in dose under observation. If the subject tolerates the dose reduction (ie, shows no or only mild symptoms that are assessed as tolerated), then the subject is to remain at the reduced dose level for ≥ 2 weeks before returning to the CRC to attempt dose re-escalation. If the subject does not tolerate the reduced dose, then the subject is to be considered an escalation failure non-responder.

Severe symptoms requiring 0 to 1 dose of epinephrine: If a subject experiences severe symptoms requiring 0 to 1 dose of epinephrine, the procedure is to have the subject return to the CRC for the next dose and to reduce the dose by 2 dose levels. If no or mild symptoms (assessed as tolerable) occur, dosing may proceed at the reduced level for at least 2 and up to 4 weeks. If moderate or severe symptoms occur, dosing is to be discontinued.

Severe symptoms requiring 2 doses of epinephrine: If a subject experiences severe symptoms requiring 2 doses of epinephrine, the procedures outlined in the above paragraph should be followed; however, dosing will proceed at the reduced dose level (if tolerated) for at least 6 and up to 8 weeks.

For specific questions related to dose-escalation or continuation of the same dose that are not answered in the above protocol, the Medical Monitor will be available for consultation.

6.5.5.1.2 Up-dosing: Tolerability Uncertain or No Tolerability at First Dose at New Dose Level

If a subject has symptoms in the CRC after up-dosing that suggest the dose was not tolerated, or suggest that tolerability of the dose is uncertain, the investigator must assess the tolerability, as outlined in [Section 6.5.3](#). The algorithm for management of dose adjustments due to poorly tolerated doses is depicted in [Figure 3](#). Explanatory text follows the figure.

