7.8.2 Individual Stopping Rules

Individuals may stop the study at any time by withdrawing their consent if they experience subjectively intolerable AEs, dosing symptoms, or for any other reason. Because ARC004 is exploring alternative dosing schedules, the approach to individual stopping rules caused by dose-related AEs varies by regimen. All subjects discontinuing the study early and permanently discontinuing AR101 treatment will return to the CRC for an Early Discontinuation Visit no later than 14 days after the last AR101 exposure.

QD Dosing Regimens

When on QD dosing regimens (including Up-dosing and Maintenance for Group 1, and QD EM for both Groups, as applicable), 7 or more consecutive days of missed daily dosing due to non-compliance constitutes an individual stopping rule. During Up-dosing, Group 1 subjects must halt up-dosing and re-start with a reduced dose if more than 4 days of dosing are missed. Missing 3 or more consecutive days on 3 occasions while on daily dosing in any period is an individual stopping rule, as is missing 15 or more consecutive days of QD dosing for any reason.

QOD, BIW, QW, or QOW Regimens

Any subject receiving nondaily dosing (QOD, BIW, QW, or QOW) who has 1 related SAE; 1 related AE graded severe; 2 related AEs occurring on separate occasions, both graded moderate; or 3 consecutive doses judged “not tolerated” will be considered as a treatment failure and discontinued from ARC004 for safety reasons. Such subjects may be eligible to enroll in ARC008 and receive AR101 daily in the Repeat Up-dosing period. If ARC008 is not available, the subjects will begin daily dosing and have visits in the Repeat Up-dosing period in ARC004. Once the subject reaches the target dose of 300 mg daily and maintains that dose for 2 weeks, that subject will be able to continue this dose regimen until ARC008 is available.

Occurrence of any of the following will result in the cessation of dosing and the subject being discontinued from the study as an escalation failure nonresponder:

- Failure to accomplish up-dosing of study product after 3 attempts
- Failure to identify a tolerated dose of study product after 3 attempts at dose reduction

Finally, administration of 3 or more doses of epinephrine for the treatment of any dose-related allergic reaction in any subject during any period is an individual stopping rule.

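### Protocol Table 7 tells sites to discontinue after exactly 2 epinephrine doses for one reaction, where the rest of the protocol stops only at 3 or more

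*Protocol*

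**What the plan says.** Five places in the Protocol deal with repeated epinephrine for one reaction.

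- **Section 6.5.6, Table 7** (what to do after treating a reaction in Up-dosing). The row "Epinephrine: ≥ 2 doses taken either in CRC or at home" has the action of discontinuing dosing, followed by an Early Discontinuation Visit.
- **Section 6.5.6, explanatory text under Table 7.** It is a reaction "that requires more than 2 doses of epinephrine will halt all further dosing of study product for the individual".
- **Section 7.8.2, Individual Stopping Rules.** The rule is "administration of 3 or more doses of epinephrine for the treatment of any dose-related allergic reaction in any subject during any period".
- **Section 6.5.5, dose adjustment.** Staying on a dose 2 levels lower for at least 6 weeks before trying to re-escalate "is mandatory if 2 doses of epinephrine are given to treat a single AE".
- **Section 6.5.5.1.1, severe symptoms.** After a decision with the Medical Monitor that the subject may continue, the next dose is given in the clinic, 2 levels lower. When 2 doses of epinephrine were needed, "dosing will proceed at the reduced dose level (if tolerated) for at least 6 and up to 8 weeks". The accompanying limit is: "If moderate or severe symptoms occur, dosing is to be discontinued".

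The Up-dosing rules also govern daily dosing later on. In Section 6.5.7, the Table 8 entry for daily regimens is "Follow Up-dosing procedures".

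**The concern.** A threshold for stopping treatment after a serious allergic reaction should be the same wherever a site looks it up. Here the table and the text written to explain it give different answers for exactly 2 doses, and the formal stopping rule agrees with the text.

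What is at stake is mainly the individual subject. Under Table 7 treatment ends; under the other sections it can continue at a lower dose. There are also consequences for the analysis:

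- A subject withdrawn for an adverse event counts as a failure under Section 7.8.3.
- The Early Discontinuation Visit has no food challenge (Section 6.3.10).
- A Group 2 subject withdrawn this way therefore has no evaluable challenge in this study. That subject drops out of the Completer population (SAP 4.2), which is used for the food-challenge summaries (SAP 9.1).
- The same holds for a Group 1 subject withdrawn before the maintenance challenge, but not for one withdrawn later.

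**Working it through.** **Step 1. Compare the rules by number of doses given for one reaction.**

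| Doses | Table 7 | Text under Table 7 | 7.8.2 | 6.5.5 and 6.5.5.1.1 |
|---|---|---|---|---|
| 1 | No stop | No stop | No stop | Reduced dose, 2 to 4 weeks |
| 2 | Discontinue | No stop triggered | No stop triggered | 2 levels lower, at least 6 weeks (6 to 8 weeks if severe and tolerated) |
| 3 or more | Discontinue | Stop | Stop | Not addressed by dose count |

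The rules part only in the middle row. Outside Table 7 they form a graded ladder: a short reduction, then a long reduction, then a stop. Table 7 removes the second step.

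**Step 2. Check whether Table 7 could be counting doses across reactions.** Its title refers to one reaction. Separate rows cover a second and a third consecutive need for epinephrine, and the second-time row continues dosing at a reduced level for 6 to 8 weeks. If the 2-dose row were cumulative, that second-time row could never apply. So the row concerns a single reaction.

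**Step 3. Look for other uses of the threshold.** Section 7.6.3 expedites an anaphylaxis report to the Safety Monitoring Committee when more than 2 doses are given for the same episode. This agrees with the text and with 7.8.2, not with Table 7.

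**Step 4. Ask who would stop under either version.** Some subjects would:

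- those meeting Section 4.3.1 (life-threatening, or severe and needing intensive therapy or recurrent);
- those with stage 3 anaphylaxis (Section 6.5.6);
- those with moderate or severe symptoms at the reduced dose (Section 6.5.5.1.1).

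Two doses alone would not ordinarily bring a subject under the intensive-therapy criterion. Appendix 5, which is guidance on seriousness but describes intensive therapy in the same terms, says that 1 or 2 intramuscular injections ordinarily do not qualify.

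**Step 5. Size.** The documents give no frequency of 2-dose reactions. The effect of one withdrawal on the failure rate is 100 divided by the planned size in Section 7.8.3:

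- Cohort 1: 100/120 = 0.83 points
- Group 1: 100/130 = 0.77 points
- each arm of Cohort 3: 175/3 = 58.3 subjects, and 100/58.3 = 1.7 points

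As an assumption, take 1 to 5 such withdrawals in a cohort. The shift is then 0.8 to 4.2 points in Cohort 1, 0.8 to 3.8 in Group 1, and 1.7 to 8.6 in one Cohort 3 arm. These are upper bounds, because some of the subjects would have stopped anyway.

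**The case against.** **Stopping at 2 doses breaks no other rule.** The text under Table 7 and Section 7.8.2 say when dosing must end, not that it must continue. The options in Section 6.5.5 are at the investigator's discretion and include stopping. The mandatory element there is the length of the hold before re-escalation. This is right, and a reader who infers that sites cannot comply with both versions goes too far: a site that withdraws every 2-dose subject complies with all of them. The conflict remains, because a site that continues a subject under 6.5.5 or 6.5.5.1.1 breaches Table 7.

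**It may be one misread symbol.** This cannot be excluded. The supplied text gives one 443 mg threshold as strictly greater in the Synopsis and as greater or equal in Section 3. But the text as supplied reads greater than or equal to 2, and both symbols appear distinctly nearby (Table 8 and Section 6.6). If the source reads more than 2, Table 7 would simply have no row for exactly 2 doses.

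**The document largely resolves it.** The explanation, the stopping rule and the committee trigger all point to 3 or more, and the Medical Monitor is available for questions. That shows which version is probably meant. It does not help a site that works from the table.

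**Wider reach.** A reader might carry the point further in three ways, none of which the documents support well.

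- *Repeat Up-dosing.* Most entrants already count as failures, or have had their exit challenge or had it omitted (Sections 3.1.5 and 7.8.3). A later 2-dose reaction changes little for them.
- *Nondaily regimens.* Section 6.5.7 says: "For subjects having acute reactions to QOD, BIW, QW, or QOW doses, appropriate treatment and follow-up is to be administered per" Section 6.5.6. That concerns treatment and follow-up. Dosing on those regimens has its own row in Table 8 and its own stopping rules.
- *The 50% cohort stopping rule.* SAP 2.3 records that Cohort 3C stayed on twice-weekly dosing and Group 1 on daily dosing, and SAP 6.1 that no subject began weekly or every-other-week dosing. Tipping that rule had little left to decide.

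**Conclusion.** Wrong as written; minor. For one reaction treated with exactly 2 doses of epinephrine, Table 7 requires discontinuation. Its own explanation and Section 7.8.2 do not, and Sections 6.5.5 and 6.5.5.1.1 provide for continued dosing at a reduced level. The scope is Group 1 Up-dosing plus daily Maintenance and daily Extended Maintenance.

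The consequence is inconsistent handling of the individual subject between sites. No count of affected subjects can be given. That the effect on cohort failure rates is likely small is a judgement: it assumes that such reactions are few and that some of these subjects would stop in any case. The conclusion also assumes that the symbol in Table 7 was read correctly. If it was not, what remains is a gap in the table rather than a contradiction.

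**What to change.** 1. Check the symbol in the source file of Table 7. If it reads as supplied, change the row to more than 2 doses (3 or more).
2. In either case add a row for exactly 2 doses: reduce by 2 dose levels and hold for at least 6 weeks before re-escalation, as in Section 6.5.5. For severe symptoms, also require the Medical Monitor decision, the next dose in the clinic, and 6 to 8 weeks at the reduced dose if tolerated, as in Section 6.5.5.1.1.
3. If the sponsor intends the stricter rule, keep Table 7 and change Sections 6.5.5, 6.5.5.1.1, the explanatory text in 6.5.6, and 7.8.2 to 2 or more.
4. If dosing has ended, report how 2-dose episodes were handled. SAP 10.13 already tabulates episodes outside food challenges by number of doses (an episode being the doses within a 2-hour window) and lists all epinephrine use. SAP 10.3 lists adverse events leading to discontinuation, reduction or interruption. Link these and add a short note to the study report.

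The cost is one table cell, one added row and a memo to sites. The retrospective check uses outputs that the SAP already plans.
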